3.9. Reporting Period

The reporting periods for each phase are defined below. For subjects that entered OLE Phase, both OLE Phase and combined study period will be used in reporting.

Core Phase

Treatment period: time from first dose of study drug intake to 28 days after last dose of study drug intake in the Core Phase.

Study period: time from first dose of study drug intake to the end of Core Phase.

For subjects who entered and took any study drug in OLE Phase, the day of their first dose intake in the OLE Phase marks the end of their Core Phase treatment and study period.

OLE Phase

Treatment period: time from first study drug intake in the OLE Phase to 28 days after last dose of study drug intake in the OLE Phase.

Study period: time from first dose of study drug intake in the OLE Phase to the end of OLE Phase.

Combined Study Period

Treatment period: time from first dose of study drug intake (either HZN-825 or placebo) in the Core Phase to 28 days after the last dose in the OLE Phase.

Study period: time from first dose of study drug intake (either HZN-825 or placebo) in the Core Phase to the end of OLE Phase.

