## 9.3.2 Eligibility Criteria for the Extension Phase

## 9.3.2.1 Inclusion Criteria

Eligible subjects must meet/provide all of the following criteria:

- 1. Written informed consent.
- 2. Completed the Double-blind Treatment Period (Week 52) of the Core Phase of the trial; subjects prematurely discontinued from trial drug in the Core Phase of the trial for reasons other than safety or tolerability may be included at the discretion of the Investigator after completing scheduled visits, including Week 52 assessments.
- 3. Willing and able to comply with the prescribed treatment protocol and evaluations for the duration of the Extension Phase of the trial.

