4.2. Extent of Study Drug Exposure and Compliance

Extent of exposure to study drug will be examined by assessing the total duration of exposure to study drug and the level of adherence to the study drug specified in the protocol for each study phase and combined periods.

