4.2.1. Duration of Exposure to Study Drug

Total duration of exposure to study drug, defined as last dosing date minus first dosing date plus 1, regardless of any temporary interruptions in study drug administration, will be summarized by treatment groups using descriptive statistics. Handling of missing last study drug dosing date will be described in the TLF shells document.

Version 2.0

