7.1.5. Summaries of Adverse Events and Deaths

Treatment emergent adverse events (TEAEs) are defined as adverse events occurring or worsening after the first dose of trial drug through 28 days after the last dose. For those patients who entered OLE Phase, date of their first dose in OLE Phase marks the end of reporting period for Core Phase.

Version 2.0

Prior AEs are defined as any AE with a start date prior to the date of first dose of study treatment. Prior AEs will not be summarized, but will be included in listings.

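### Combined-period exposure and treatment-emergent events run across the off-drug gap of subjects who stopped drug early in the Core Phase and later entered the extension

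*SAP*

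**What the plan says.** **Who can have a gap.** Protocol 9.3.2.1, criterion 2, states that "subjects prematurely discontinued from trial drug in the Core Phase of the trial for reasons other than safety or tolerability may be included" in the extension, at the investigator's discretion and once visits through Week 52 are complete. Protocol 9.3.3 asks early stoppers to stay in the trial and keep attending visits. Months off drug followed by open-label dosing is therefore a foreseen path.

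**Combined period.** SAP 3.9 defines the combined treatment period as running from the first dose "in the Core Phase to 28 days after the last dose in the OLE Phase". SAP 4.2.1 gives one exposure formula, "defined as last dosing date minus first dosing date plus 1, regardless of any temporary interruptions in study drug administration". SAP 4.2 asks for duration of exposure and "the level of adherence to the study drug specified in the protocol for each study phase and combined periods". SAP 7.1.5.1 reports adverse events, many with exposure-adjusted rates, for each phase and for the combined periods.

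**Core Phase.** SAP 3.9 first sets the treatment period as "time from first dose of study drug intake to 28 days after last dose of study drug intake in the Core Phase". For subjects who took extension drug it then adds that "the day of their first dose intake in the OLE Phase marks the end of their Core Phase treatment and study period". SAP 7.1.5 has the same structure. Treatment-emergent events are "adverse events occurring or worsening after the first dose of trial drug through 28 days after the last dose", followed by: "For those patients who entered OLE Phase, date of their first dose in OLE Phase marks the end of reporting period for Core Phase".

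**Protocol rules on the same matter.** Protocol 9.5.5.1.2 ends the treatment-emergent period 4 weeks after the last dose or premature discontinuation. Protocol 9.6.1.6 and 9.6.2.4 define event rates per patient-year of follow-up while dosing. SAP 2.5, which lists departures from the protocol's planned analyses, does not mention this one.

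**The concern.** The combined rules use only the two outer dates: the first Core dose and the last extension dose. They give the right answer for a subject who goes straight from blinded to open-label drug. They give the wrong answer for a subject with a long untreated interval between the two. An adverse event months after the last Core dose and before the first open-label dose is then a combined-period treatment-emergent event, and the untreated months are added to exposure.

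What is at stake is the combined safety and exposure reporting. Its rates would mix on-drug and off-drug events and time, and only for early stoppers who chose to continue. This conflicts with the protocol's dosing-based rate definition.

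The Core wording adds an ambiguity. Neither SAP 3.9 nor 7.1.5 says that the earlier of the two end dates applies. Taken literally, the extension-entry sentence moves the end of an early stopper's Core treatment period out to the first open-label dose. The same off-drug event would then be a Core treatment-emergent event in a subject who later enters the extension and not in one who does not.

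**Working it through.** The documents state no figure for the gap, so there is nothing to reproduce. The check applies the SAP's date rules to one subject.

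**Inputs**
- Exposure = last dosing date − first dosing date + 1 (SAP 4.2.1), reported for the combined periods (SAP 4.2).
- Combined treatment period ends at last extension dose + 28 days (SAP 3.9).
- Base Core treatment period ends at last Core dose + 28 days (SAP 3.9).
- Assumed dates: first Core dose Day 1, first open-label dose Day 365, last open-label dose Day 728 (364 dosing days). Last Core dose on Day L = 7 × stop week, with the stop week varied because the documents do not give it.

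**Formulas**
- Counted combined exposure = 728 − 1 + 1 = 728 days, whatever L is.
- Days of dosing = L + 364.
- Off-drug gap = 365 − L − 1 = 364 − L.
- Gap beyond the 28-day tail, before the first open-label dose = 364 − L − 28.
- Combined treatment period under the SAP = 728 + 28 = 756 days. With the gap beyond the tail removed = (L + 28) + (364 + 28).

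| Core stop | L | Gap | Dosing days | Counted exposure | Excess | Gap days beyond tail | Treatment period, SAP → gap removed |
|---|---|---|---|---|---|---|---|
| Week 12 | 84 | 280 | 448 | 728 | 728/448 = +62.5% | 252 | 756 → 504 |
| Week 20 | 140 | 224 | 504 | 728 | 728/504 = +44% | 196 | 756 → 560 |
| Week 28 | 196 | 168 | 560 | 728 | 728/560 = +30% | 140 | 756 → 616 |
| Week 40 | 280 | 84 | 644 | 728 | 728/644 = +13% | 56 | 756 → 700 |

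For exposure, the whole gap is excess. For the treatment period, only the part beyond 28 days is excess, because the SAP's own base rule counts the tail as treatment.

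**Scale in a group.** Take the planned arm of 45, assume all enter the extension, and let 44 be dosed for the full 728 days. One Week 12 stopper then adds 280 days to a true total of 45 × 728 − 280 = 32,480 days, which is 0.9%. With fewer entrants, or with more such subjects, the share rises.

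**Core Phase.** For a Week 12 stop, the base rule ends the treatment period on Day 84 + 28 = 112; the literal reading of the extension-entry sentence ends it on Day 365. Core exposure under the SAP 4.2.1 formula still ends at the last Core dose (84 days). On that reading, gap events would enter the Core count while gap time would not enter Core exposure.

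**The case against.** The strongest reply concerns the Core sentence. It follows a base rule of last Core dose plus 28 days. For an ordinary entrant that date falls after the first open-label dose, so the sentence most naturally shortens the period. SAP 6.1.1.4 supports this, since it describes the treatment period as last dose plus 28 days with no exception for extension entrants. This stands. A reader might infer that the SAP deliberately extends the Core treatment period of early stoppers, but the text only leaves that reading open.

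A reader might also infer that Core event rates are pulled toward the untreated rate. The documents do not support that. The only exposure formula, applied to the Core Phase, stops at the last Core dose and so excludes the gap. On the literal reading, gap events would be counted without gap time. The SAP also does not define the rate denominator, so no direction should be claimed for Core rates.

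For the combined period, a continuous window has some protocol basis: a footnote to the Core schedule of assessments (2.1) treats events through the Safety Follow-up Visit as treatment-emergent. However, Protocol 9.5.5.1.2 adds premature discontinuation as an end point. Phase-specific tables, doses administered, adherence and full listings make the problem visible but do not correct the combined tables. The SAP's reference to temporary interruptions is no answer either: a stop followed by a restart in the extension is not clearly a temporary interruption, and the formula spans the gap in any case. Further conventions sit in the TLF shells, which are not part of these documents.

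Finally, safety reporting is descriptive, and the affected group is limited by the entry conditions in a trial of about 135. Both points limit the consequence.

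**Conclusion.** The point holds for the combined period. As written, SAP 3.9 and 4.2.1 count the off-drug gap as treatment and as exposure, and nothing in the SAP text removes it. For one subject with 52 weeks of open-label drug, the excess exposure is 62.5%, 44%, 30% or 13% for a Core stop at Week 12, 20, 28 or 40. The off-drug days wrongly inside the combined treatment period are 252, 196, 140 or 56. These figures rest on the assumed dosing dates. They describe one subject and should not be read as the error in a group rate, which depends on an unstated and probably small number of such subjects.

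For the Core Phase, the finding is an ambiguity. The sentence was probably meant as a cap, but without wording to that effect a programmer could follow it literally and make Core treatment-emergent status depend on later extension entry.

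The impact is confined to descriptive safety and exposure tables. The primary FVC analysis does not use these periods, and the on-treatment supplementary analysis sets its own limit of last dose plus 28 days, so efficacy results do not change. The SAP should be corrected, but the point does not threaten the trial's main conclusions.

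**What to change.** - In SAP 3.9 and 7.1.5, end the Core treatment period at the earlier of last Core dose plus 28 days and the first open-label dose. If a cap was intended, this only records it.
- In SAP 3.9, define the combined treatment period as the union of the Core and extension treatment periods, and apply the same limits to combined treatment-emergent events in 7.1.5.
- In SAP 4.2.1, define combined exposure as Core duration plus extension duration, counting once any date that carries both the last Core dose and the first open-label dose.
- List adverse events in the gap as off-treatment, so that they remain visible.

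The cost is a few sentences in the SAP and a small programming change, with no new data. Combined exposure becomes slightly shorter. A subject dosed continuously into the extension is unaffected: 364 + 364 = 728 days, as now.

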1.1.2. Part 2 (Extension Phase)

The overall objective of the Extension Phase is to investigate the long-term efficacy, safety and tolerability of HZN-825, a selective antagonist of LPAR1, administered at a dose of 300 mg BID to subjects with IPF in a 52-week OLE following completion of the Core Phase of the trial. The dose for the Extension Phase may be modified based on the results of the Core Phase.

Two types of Baseline are defined for the Extension Phase:

- OLE Baseline, defined as the latest measurement prior to the first dose of HZN-825 in Extension Phase
- HZN-825 Baseline, defined as the latest measurement prior to the first dose of study drug (either HZN-825 or Placebo) in the Core Phase

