3.1.4. OLE Phase Analysis Set

The OLE Phase Analysis Set (OLE-SAF) includes all subjects that are enrolled in OLE Phase and took at least 1 dose of study drug during the OLE Phase. This analysis set will be the

Version 2.0

primary analysis set for both efficacy and safety for the OLE Phase and combined periods. Subjects will be analyzed by actual treatment received in Core Phase.

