7. SAFETY ANALYSES

Safety outcomes will be summarized descriptively for each study phase and combined periods. No inferential statistics are planned for safety outcomes. Safety analyses will be based on the Safety Analysis Set for the Core Phase, and OLE-SAF set for the OLE Phase and the combined periods.

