7.1.5.1. Summaries of AE Incidence

The incidence of following AEs will be summarized by SOC, PT, and treatment group for each study phase and the combined periods. Number and percentage of subjects who experienced events will be reported. AE summaries followed by an asterisk(*) will include the number of events and the corresponding exposure adjusted incidence rate:

- 1 TEAEs*
- 2 RCTC Grade 3 or higher TEAEs*
- 3 Serious TEAEs*
- 4 Treatment-related TEAEs*
- 5 TEAEs by maximum severity
- 6 Treatment-related TEAEs by maximum severity
- 7 Serious treatment-related TEAEs*
- 8 TEAEs assessed by the investigator as representing respiratory deterioration*
- 9 TEAEs assessed by the investigator as IPF-disease related*
- 10 TEAEs leading to permanent withdrawal of any trial drug*
- 11 TEAEs leading to death (ie, outcome of death)*
- 12 Subject incidence of AESIs: Orthostatic hypotension

Additionally, the frequency of TEAEs occurring in > 5% of subjects in any treatment group, serious TEAEs occurring in >3% of subjects in any treatment group, treatment-related serious TEAES occurring in >=2% of subjects in any treatment group, will be summarized by treatment group, primary SOC, and preferred term.

Multiple events will be counted only once per subject in each summary of subject counts. Adverse events will be summarized and listed first in alphabetic order of SOC and then by PT in descending alphabetical order within each SOC. For summaries by severity, the most severe severity will be used for those AEs that occurred more than once in a given subject during the trial.

In addition to the above summary tables, TEAEs and treatment-related TEAEs will be summarized by PT only in descending order of total frequency.

Version 2.0

In addition, data listings will be provided for the following:

- All AEs, indicating whether the event is treatment emergent
- SAEs
- Treatment-related serious TEAEs and non-serious TEAEs
- Deaths
- AEs leading to permanent withdrawal of trial drug
- Adjudicated AEs
- Adverse events of special interest: Orthostatic hypotension

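### The combined 104-week safety tables leave out Core-Phase safety withdrawals and deaths but keep the OLE entrants' Core person-time, and one column mixes placebo with HZN-825 time

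*SAP*

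**What the plan says.** SAP 3.9 defines a combined period for subjects who entered the OLE. It opens with "Treatment period: time from first dose of study drug intake (either HZN-825 or placebo) in the Core Phase" and closes 28 days after the last OLE dose. SAP 7 assigns the populations: "Safety analyses will be based on the Safety Analysis Set for the Core Phase, and OLE-SAF set for the OLE Phase and the combined periods". SAP 3.1.4 says that OLE-SAF "includes all subjects that are enrolled in OLE Phase and took at least 1 dose of study drug during the OLE Phase", and for the columns: "Subjects will be analyzed by actual treatment received in Core Phase". The combined tables therefore have a QD, a BID and a placebo column, named after the Core arm.

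SAP 7.1.5.1 states: "The incidence of following AEs will be summarized by SOC, PT, and treatment group for each study phase and the combined periods". Most rows, including TEAEs leading to withdrawal and fatal TEAEs, carry an exposure-adjusted incidence rate as well as subject counts. No person-time formula is given. Patient-years of exposure appears only in the abbreviation list, and SAP 4.2.1 measures exposure from first to last dosing date, ignoring interruptions.

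Entry to the OLE is selective. Under Protocol 9.3.2.1 a subject must have completed the double-blind period, with one exception: "subjects prematurely discontinued from trial drug in the Core Phase of the trial for reasons other than safety or tolerability may be included", at the investigator's discretion and after the Week 52 assessments.

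**The concern.** SAP 1.1.2 states that the Extension Phase is to "investigate the long-term efficacy, safety and tolerability of HZN-825". The combined tables are the only ones planned to span 104 weeks, so they are the ones likely to be read as the long-term safety result.

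Two features make that reading unsafe. First, the tables select on having reached the OLE without a safety stop, yet count person-time from the start of the Core Phase. This is immortal time for withdrawal and death. Second, subjects randomised to placebo bring a placebo year into a column whose later year is on HZN-825. Neither feature is flagged in the SAP, and no single planned table covers all HZN-825 exposure. Protocol 7.1.3.5 lists transaminase increase as an important identified risk, so a complete account of who stopped drug for safety matters to the benefit-risk reading.

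**Working it through.** The documents give no event or discontinuation rate, so there is no planned figure to reproduce. The rates below are assumptions shown over a range. Inputs from the documents: 45 subjects per arm (SAP 1.3), 1:1:1 allocation and 52 Core weeks (Protocol 9.4.1), and 52 OLE weeks, giving 104 in total (Protocol synopsis, Trial Design).

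**1. Who can contribute a withdrawal or death**

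- Core safety or tolerability stop: not eligible for the OLE, so not in OLE-SAF and not in a combined table.
- Core death: same result.
- OLE entrant: in the table, with a full Core year in the denominator during which neither event can have happened.

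The combined numerator for these two rows is in effect the OLE numerator. The exception is an event with Core onset that leads to withdrawal or death only after OLE entry.

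**2. Size of the omission (QD and BID arms together, n = 90)**

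Assume that a fraction d stops for safety in the Core Phase at mean week 26, that everyone else enters the OLE, and that a fraction o of entrants stops at mid-OLE. Ignore the 28-day tail. Per subject:

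- Core table: d / (1 − d/2)
- OLE table: o / (1 − o/2)
- Combined table: o / (2 − o/2)
- All treated: [d + (1 − d)o] / [(1 − d)(2 − o/2) + d/2]

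For d = 10% and o = 5%: 9 Core stops and 81 entrants, of whom 4.05 stop. OLE time is 76.95 + 2.025 = 78.975 patient-years. Combined: 4.05 / (81 + 78.975) = 2.5 per 100 patient-years. All treated: 13.05 / (81 + 4.5 + 78.975) = 7.9.

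Withdrawals per 100 patient-years:

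| d | o | Core | OLE | Combined | All treated |
|---|---|---|---|---|---|
| 5% | 0 | 5.1 | 0 | 0 | 2.6 |
| 10% | 0 | 10.5 | 0 | 0 | 5.4 |
| 20% | 0 | 22.2 | 0 | 0 | 11.8 |
| 5% | 2.5% | 5.1 | 2.5 | 1.3 | 3.9 |
| 10% | 5% | 10.5 | 5.1 | 2.5 | 7.9 |
| 20% | 10% | 22.2 | 10.5 | 5.1 | 16.9 |

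In the lower three rows the combined rate lies below both the Core rate and the OLE rate. No valid pooling of the two phases could give that.

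**3. Placebo time**

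If all complete 104 weeks, the placebo share is 52/104 = 50% in the placebo-to-BID column, 52/312 = 16.7% in a column pooling the three arms, and 0% in the QD and BID columns.

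Let RR be the on-drug rate divided by the placebo rate, with one on-drug rate throughout. The displayed rate relative to the on-drug rate is 0.5 + 0.5/RR in the placebo-to-BID column and 5/6 + 1/(6·RR) in a pooled column.

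| RR | Placebo-to-BID | Pooled |
|---|---|---|
| 0.7 | 1.21 | 1.07 |
| 1 | 1.00 | 1.00 |
| 1.5 | 0.83 | 0.94 |
| 2 | 0.75 | 0.92 |
| 3 | 0.67 | 0.89 |

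**The case against.** A sponsor could answer that nothing is hidden. The Core tables use everyone dosed in the Core Phase (SAP 3.1.3 and 7), so Core safety withdrawals appear there, in the listings of withdrawals and deaths (SAP 7.1.5.1), and in the disposition summary by phase (SAP 4.1). The first OLE dose ends the Core period, so the Core and OLE tables together cover all HZN-825 exposure without overlap. Safety is descriptive, and following each randomised arm for 104 weeks is a legitimate display. All of this stands, and it is why the existing tables should stay. It does not repair the combined withdrawal and fatal-event rates, which cannot be read as 104-week rates.

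Several stronger readings are tempting, but the documents do not support them:

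- *Long-term event rates are understated in general.* Placebo time touches only the placebo-to-BID column or a pooled column, and its direction depends on RR. For events other than withdrawal and death, the effect of the exclusion depends on how the excluded subjects differ, which is unknown.
- *Placebo time dilutes every measure.* Only exposure-adjusted rates can be diluted. For a percentage of subjects, an added placebo year can only raise the figure. The orthostatic hypotension and severity tables carry no such rate.
- *Placebo time dilutes the liver table.* SAP 7.2.2 counts subjects at their worst value, not per patient-year. It also names the Safety Analysis Set as denominator, whereas SAP 7 assigns OLE-SAF to the combined period. The SAP should say which applies.
- *A pooled rate is planned.* Protocol 9.6.2.2 has an overall group for its Extension Phase sets, but the SAP safety text names none for the combined period.
- *Core safety withdrawals cannot appear at all.* This is true only of the combined tables.

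**Conclusion.** The point holds in a limited form. The combined rates of TEAEs leading to withdrawal and of fatal TEAEs are understated in all columns by the way population and period are defined. No assumption about relative risk is needed, only that such events occur in the Core Phase. Under the assumed stopping fractions, the combined withdrawal rate is between zero and about a third of the all-treated rate. Subjects who finish the Core Phase and decline the OLE would add event-free time to the all-treated denominator and narrow the gap; they are not modelled.

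The mixing of placebo and active time is a separate and smaller matter: one column, exposure-adjusted rates only, in either direction. Its size assumes full completion and a constant on-drug rate. Both parts infer the rate denominator from SAP 3.9 and 4.2.1, because the SAP does not state it.

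No alpha or power is affected. The remaining gap is that no single table integrates all HZN-825 exposure.

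**What to change.** In SAP 3.1, 3.9 and 7, add an all-HZN-825-exposed set: every subject with at least one dose of HZN-825 in either phase, counted from the first HZN-825 dose (Core Day 1 for QD and BID, first OLE dose for placebo subjects) to 28 days after the last.

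- **Columns:** QD-to-BID, BID-to-BID, placebo-to-BID (from the first OLE dose), and overall. Subjects who never enter the OLE stay in the column of their Core regimen.
- **Denominator:** patient-years on HZN-825, with the formula written out. State how off-drug gaps are handled for subjects who stopped early for non-safety reasons and restart in the OLE, since SAP 4.2.1 ignores interruptions.
- **Scope:** TEAEs, withdrawals, deaths and the liver thresholds, with the denominator in SAP 7.2.2 stated for each period.
- **Existing combined tables:** keep them by Core arm, with a footnote that they cover OLE entrants only and include placebo time in the placebo column.

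The cost is one population flag, one extra set of tables and a few lines of SAP text. No new data are needed. The reported long-term withdrawal and death rates may be higher.
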